2.3 Benefit/Risk assessment

Potential risks are based on the mechanism of action, the nonclinical toxicology data, and the safety data from the FIH study.

LTP001 is the first SMURF1 inhibitor to be developed. Based on current understanding of SMURF1 biology, there are no concerns directly related to this mechanism of action; and, because LTP001 is first-in-class, there are no previously identified clinical safety risks (i.e., no known class effects).

Preclinical data

CCI

CCI

Clinical data

Single doses of LTP001 CCI mg, CCI mg, CCI mg, CCI mg, CCI mg and CCI mg were well tolerated and did not show safety signals for LTP001 in the first in human study.

Multiple doses of LTP001 CCI mg, CCI mg, CCI mg, CCI mg and CCI mg once daily and CCI mg bid were well tolerated. CCI

CCI , clinical laboratory assessments, ECGs, and vital signs did not show significant abnormalities. CCI

The risk to participants in this trial will be minimized by adherence to the eligibility criteria, close clinical monitoring, regular safety data reviews, and pre-specified rules for automatically stopping the study should unanticipated safety issues suddenly arise.

No reproductive toxicology studies have been performed for LTP001. Women of child-bearing potential will be only enrolled if they use highly effective contraception methods.

Additional details about potential risks of LTP001 can be found in the Investigator's Brochure.

Procedural risks

Cardiac catheterization is a safe procedure when performed by an experienced medical team. However, there may be some possible risks such as bleeding, infection, and blood clots. A heart attack or a stroke can happen in very rare situations. Right heart catheterization (RHC) is regularly employed to monitor the course of PAH. RHC may be performed without radiation but for optimal placement of the catheter, the investigator can employ x-ray to double-check the positioning of the catheter when measurements are made. RHC does not employ contrast media. RHC is required to calculate PVR. PVR was the primary efficacy assessment of the

parent study, CLTP001A12201, and is performed at Week 26 in the current study, which allows the assessment of the 1-year effect of LTP001 of those participants who received LTP001 already in the parent study, and the 6-month effect on PVR of those who received placebo in the parent study. This data is considered very important to assess the long-term effect of LTP001 on PVR in patients with PAH.

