The safety and efficacy of LTP001 will be checked at the following visits: Weeks 5, 13, 26, 39 and 52, as specified in the Assessment Schedule. Safety and tolerability assessments will take place at each visit. RHC will be performed at week 26, 6MWT and echocardiography will be assessed at Weeks 26 and 52. PAH-SYMPACT and emPHasis-10 will be collected for 7 days intervals with the seventh day of collection occurring within the allotted visit window for all Treatment visits (Weeks 5, 13, 26, 39 and 52). Participants will have safety follow-up phone calls at Weeks 9 and 17, and may be invited for safety assessment at site if deemed necessary. The PI may exercise their discretion in which safety assessments are required at these optional safety follow-up visits. Following the end of treatment period, participants will have one safety follow-up phone call approximately 30 days after the end of treatment visit at Week 52. The duration of the extension study is currently restricted to 52 weeks, but the study may be prolonged (via an amendment to the protocol) if the LTP001 development program in PAH continues and the benefit/risk assessment remains favorable for the patient population studied. The safety and efficacy profile of LTP001 that is observed in this extension study as well as the parent study, CLTP001A12201, will determine continuation of the extension study.

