9.4 Secondary endpoint(s)/estimand(s) analysis

9.4.1 Efficacy and/or pharmacodynamic endpoint(s)

Change from baseline for efficacy endpoints including the right heart catheterization (RHC) parameters, 6-Minute Walk Distance (6MWD), and N-terminal fragment of the prohormone B-type natriuretic peptide (NT-proBNP) will be descriptively summarized by visit/time for treatment group (treatment received in the parent study), and overall. The baseline measurement for the extension will be the baseline measurement taken during the parent study CLTP001A12201. Graphs (e.g., spaghetti plot) will be provided to show individual time courses of parameters for the extension study together with the parent study.

Additionally, changes from baseline for efficacy endpoints will be descriptively summarized by visit/time for treatment group (treatment received in the parent study), and overall using a different baseline strategy: participants receiving LTP001 in the parent study will use the baseline of parent study as the baseline; participants switching from placebo in parent study to LTP001 in extension study will use the baseline of extension study as the baseline.

Time to clinical worsening will be analyzed using survival analysis (i.e., Kaplan-Meier) and the corresponding 80% confidence interval will be computed using the appropriate method.

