1.1 Study design

This is a non-randomized, open-label extension study over 52 weeks with LTP001 without a control treatment arm. Participants will be presented the opportunity to consider the extension study at the End of Treatment (EOT) visit (Week 25) of the parent study CLTP001A12201. The investigator will assess if the participant will continue by verifying that the participant has completed the parent study as planned. Moreover, at the EOT the investigator will determine the eligibility for the extension study (i.e. that none of the treatment discontinuation criteria were met and that the assessments at the EOT of the parent efficacy study were completed according to the parent protocol). The patient may directly continue into the extension study. If the patient does not directly continue in the extension study, the time between the end of treatment assessments in the parent study and the enrollment in the extension study i.e. during the transition period should be kept to a minimum (it should not exceed 14 days).

In case of a direct transition into the extension study after the end of treatment visit in the parent study, as not all assessment results will be available (e.g. the central lab assessments) at the same day the investigator will re-assess/reconfirm the eligibility as soon as outstanding results are received.

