2.6.1.1 Efficacy and/or pharmacodynamic endpoints(s)

All analyses will be conducted using PD analysis set.

Change from baseline for efficacy endpoints will be descriptively summarized by visit/time for treatment group assigned in the parent study, and overall. Two baseline measurements will be generated as per [Section 2.1.1](#). Graphs (e.g., spaghetti plot) will be provided to show individual time courses of parameters for the extension study together with the parent study.

Additionally, two changes from baseline values for efficacy endpoints will be descriptively summarized by visit/time for treatment group assigned in the parent study, and overall with the following comparisons:

- a) Short-term (change from baseline of extension study) vs. long-term (change from baseline of the parent study) treatment effect (For both treatment and placebo groups assigned in the parent study).
- b) the treatment group difference (assigned in the parent study) within each change from baseline value.

6MWD

This measures how many meters a person can walk in 6 minutes. It includes total distance walked (6MWD), the number and duration of any stops in 6 minutes. Test performed at baseline and at visits on Day 176 and 358 will be used for analysis.

Descriptive statistics (N, mean, SD, CV% mean, geometric mean, CV% geometric mean, median, min, and max) summarizing 6MWD parameters and their changes from baseline will be summarized by visit/time for treatment group assigned in the parent study and overall.

Panels of individual spaghetti plots over time/visit for treatment group assigned in the parent study and overall for each 6MWD parameter will be provided.

All 6MWD parameters will be listed by participant, and visit and if ranges are available, abnormalities will be flagged.

RHC

The RHC is performed to assess several hemodynamic parameters when the patient is in a stable hemodynamic rest state (as demonstrated by three consecutive cardiac output measurements with 10% of each other). The measurement is taken at baseline and at visit on Day 176. The assessed hemodynamic parameters include:

- PVR
- right atrial (RA) pressure
- mean pulmonary artery pressure (mPAP)
- pulmonary capillary wedge pressure (PCWP)
- systolic and diastolic blood pressure (RV pressures)
- heart rate (HR)
- cardiac output (CO)
- systemic vascular resistance (SVR)
- mixed venous blood gas measurement

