- Significant drop in 6MWD (15% from baseline or more) due to PAH-worsening

Time to clinical worsening will be analyzed using survival models (i.e., Kaplan-Meier, cox regression) if adequate number of events occur during the study to characterize the survival curve. Participants without the event will be considered as censored at the end of the time at risk. The hazard ratio between the treatment group assigned in the parent study and the corresponding 80% confidence intervals will be computed using the appropriate method. If there is no adequate number of events, the number (and percentage) of participants with clinical worsening will be summarized by treatment group assigned in the parent study and overall.

NT-proBNP

Descriptive statistics (N, mean, SD, CV% mean, geometric mean, CV% geometric mean, median, min, and max) summarizing N-terminal fragment of the prohormone B-type natriuretic peptide , NT-proBNP (visits on Day 29, 85, 176, 267 and 358) and its changes from baseline will be summarized by visit/time for treatment group assigned in the parent study and overall.

Spaghetti plot over time/visit will be provided. And the endpoint will be listed by participant, and visit and if ranges are available, abnormalities will be flagged.

Change from baseline for efficacy endpoints will be descriptively summarized by visit/time for treatment group assigned in the parent study, and overall. The baseline measurement for the extension will be the baseline measurement taken during the parent study CLTP001A12201. Graphs (e.g., spaghetti plot) will be provided to show individual time courses of parameters for the extension study together with the parent study.

Additionally, changes from baseline for efficacy endpoints will be descriptively summarized by visit/time for treatment group assigned in the parent study, and overall using a different baseline strategy: participants receiving LTP001 in the parent study will use the baseline of parent study as the baseline; participants switching from placebo in parent study to LTP001 in extension study will use the baseline of extension study as the baseline.

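### The mixed-baseline overall row is pooled by extension visit, so at Week 26 it averages about a year of LTP001 in continuers with about six months in placebo switchers

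*SAP*

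**What the plan says.** Protocol 2.3 gives the Week 26 right heart catheterization (RHC) two purposes. It "allows the assessment of the 1-year effect of LTP001 of those participants who received LTP001 already in the parent study", and it gives "the 6-month effect on PVR of those who received placebo in the parent study". These are separate quantities in separate groups.

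For the efficacy endpoints, SAP 2.6.1.1 plans summaries by parent-study group and overall, from the parent baseline and from the extension baseline (both defined in SAP 2.1.1). It then adds a further set, "descriptively summarized by visit/time for treatment group assigned in the parent study, and overall using a different baseline strategy". Here parent-study LTP001 participants keep the parent baseline, while "participants switching from placebo in parent study to LTP001 in extension study will use the baseline of extension study as the baseline" (Protocol 9.4.1; the SAP says the same). In the SAP this paragraph follows the NT-proBNP text, but it is worded for the efficacy endpoints generally and matches Protocol 9.4.1, so I read it as covering all of them.

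On timing, Protocol 4.1 states: "RHC will be performed at week 26, 6MWT and echocardiography will be assessed at Weeks 26 and 52". For RHC, SAP 2.6.1.1 adds: "The measurement is taken at baseline and at visit on Day 176". The named days are those of the extension schedule. No summary is indexed by time since first LTP001 dose.

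**The concern.** The mixed strategy fixes half of an alignment problem. It starts everyone's clock at the last pre-LTP001 value, which is sensible, but it reads the clock at a common extension visit, when the two groups have been on drug for very different times. A pooled mean at that visit depends on how many continuers and switchers are in it as well as on the drug.

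In the SAP the overall row is also the only new number this strategy produces. Continuers from parent baseline and switchers from extension baseline are already covered by the two-baseline, by-group summaries. If the effect grows or wanes between 6 and 12 months, a reader who takes the overall PVR, 6MWD, echocardiography or NT-proBNP row as the LTP001 effect at Week 26 will attach it to a duration it does not represent.

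**Working it through.** **Inputs.** The parent study ends treatment "at the End of Treatment (EOT) visit (Week 25) of the parent study CLTP001A12201" (SAP 1.1). Extension Week 26 is Day 176 and Week 52 is Day 358 (Protocol Table 1-2). The transition may take up to 14 days (SAP 1.1). About 40 participants are expected (Protocol 1.1). The split between continuers and switchers is not given, so I use a continuer share p from 1/3 to 3/4. The parent day number is not given either. If the parent study numbers visits as the extension does (Week 5 = Day 29, i.e. 4 elapsed weeks), parent Week 25 is Day 169, or 24 elapsed weeks.

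**Reproducing the stated durations.** By visit label, continuers at extension Week 26 have 25 + 26 = 51 weeks (11.7 months) and switchers have 26 weeks (6.0 months), which matches the 1-year and 6-month description in Protocol 2.3. By elapsed days, (176 − 1)/7 = 25 weeks, so continuers have 24 + 25 = 49 weeks (11.3 months) and switchers 25 weeks (5.7 months). The two groups differ by 24 to 25 weeks of exposure. With a full 14-day gap, the difference in calendar time since first LTP001 is 26 weeks.

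**Mean exposure in the Week 26 overall row** = p × continuer weeks + (1 − p) × switcher weeks:

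| p | Elapsed days (49 / 25) | Visit label (51 / 26) |
|---|---|---|
| 1/3 | 33.0 | 34.3 |
| 1/2 | 37.0 | 38.5 |
| 2/3 | 41.0 | 42.7 |
| 3/4 | 43.0 | 44.8 |

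None of these is 6 months or 1 year. For endpoints also measured at Week 52 the same happens there: 24 + 51 = 75 weeks against 51 by elapsed days, or 25 + 52 = 77 against 52 by label.

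**Effect on the summary.** If the mean change is d6 at 6 months and d12 at 1 year, the row equals p × d12 + (1 − p) × d6. It misses d6 by p × (d12 − d6). The documents give no values, so these are illustrations in PVR units (dyn·s/cm⁵):

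- d6 = −100, d12 = −200: −133 at p = 1/3, −150 at p = 1/2, −175 at p = 3/4. The row moves with group share alone.
- d6 = −100, d12 = −80 (waning): −90 at p = 1/2.
- d6 = d12 = −100 (flat): −100 at any p, so no distortion.

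**What alignment on first LTP001 dose gives.**

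- 6 months: continuers at parent Week 25 (24 elapsed weeks) with switchers at extension Week 26 (25 elapsed weeks), one week apart.
- 1 year: continuers at extension Week 26 (49) with switchers at extension Week 52 (51), two weeks apart. This works for 6MWD, echocardiography and NT-proBNP. Switchers have no scheduled RHC after Week 26, so the 1-year RHC row can hold continuers only.

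**Precision of the pooled 6-month change**, with similar SDs, relative to one group alone is 1 − √(n₁/40):

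- 20:20 split: 1 − √(20/40) = 29%.
- 27:13 split: 1 − √(27/40) = 18% against the larger group, and 1 − √(13/40) = 43% against the smaller.

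**The case against.** The strongest reply is that the plan already answers its own question. The sentence that creates the overall row also creates by-group rows, and these are the 1-year change in continuers and the 6-month change in switchers. Protocol 2.3 never asks for a pooled figure. This stands, and it sets the limit of the point. A reader might infer that the purpose of the invasive RHC is missed; the by-group rows show that it is not.

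A reader might also infer that the 6-month information in continuers is lost. It is not. The parent Week 25 visit is the extension baseline, so those values stay in the analysis data. SAP 2.6.1.1 also compares change from parent baseline with change from extension baseline in each group. In continuers with complete data, the difference between those two means is the change to parent Week 25. Individual time courses are plotted across both studies.

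It is also true that nothing is tested on this row. Estimands are not applicable, efficacy is secondary, and models are foreseen only for time to clinical worsening. The emerging efficacy profile informs continuation of the study (Protocol 4.1), but no rule uses an overall mean.

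Finally, the aligned 6-month row is itself a mixture. It joins blinded parent data with open-label data, and its parent part is limited to LTP001 participants who completed and entered the extension. Keeping the groups separate is therefore a legitimate choice, and dropping the pooled row is an acceptable minimum. This does not rescue the by-visit overall row, whose value depends on group shares and which carries no caveat.

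**Conclusion.** The point holds for the overall rows under the mixed-baseline strategy. At Week 26 they combine changes after about 49 to 51 weeks of LTP001 with changes after about 25 to 26 weeks, and they describe no single treatment duration unless the effect is flat between 6 and 12 months. The documents give no figure on that time course, so the size of the distortion is unknown and could be zero. The PVR values above are only illustrative.

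The conclusion assumes that by visit means by extension visit. The term is undefined, and SAP 2.1.1 counts days both from first LTP001 and from first dose of LTP001 or placebo, but the named days match the extension schedule. The precision gain assumes the stated splits and similar SDs, and it applies to an uncontrolled within-participant change, not to a treatment effect against control.

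The primary safety analysis and the by-group efficacy results are unaffected. This is a worthwhile correction to descriptive secondary rows.

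**What to change.** In SAP 2.6.1.1, and in Protocol 9.4.1 if it is amended, index the pooled row of the mixed-baseline strategy by time since first LTP001 dose:

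- **6-month row:** parent Week 25 for continuers plus extension Week 26 for switchers.
- **1-year row:** extension Week 26 for continuers plus extension Week 52 for switchers, for 6MWD, echocardiography and NT-proBNP; continuers only for RHC.

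Keep the by-visit rows by parent-study group and drop the by-visit overall row. If re-indexing is not wanted, dropping that row is the minimum. Footnote the 6-month row to say that it mixes blinded and open-label periods and includes only parent-study LTP001 participants who entered the extension.

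The cost is SAP wording and one re-indexed table per endpoint, with no new assessments.

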2.6.1.2 Patient reported outcomes

All analyses will be conducted using PD analysis set.

PROs (emPHasis-10 and PAH-SYMPACT scores) that will be taken at Day 29, 85, 176, 267, and 358 will be summarized as the original scores, as well as change from baseline, by time/visit. The baseline measurement for the extension study will be the baseline measurement of the parent study CLTP001A12201. Missing data may be imputed using a last observation carried forward approach (LOCF) as necessary.

2.6.2 Statistical hypothesis, model, and method of analysis

Most analyses will be conducted descriptively using summary statistics and visualization of the time course for each endpoints using graphical presentations (e.g. spaghetti plots). statistical models may be used when data allows for TTCW. Detailed method of analyses are specified under each endpoint in [Section 2.6.1.1](#).

2.6.3 Handling of intercurrent events

Not applicable.

2.6.4 Handling of missing values not related to intercurrent event

See each endpoint in [Section 2.6.1](#). If not specified, missing data will not be imputed.

2.6.5 Sensitivity analyses

For the analysis of 6MWT, missing measurement will be assumed MAR. Alternative assumptions may be explored to investigate the robustness of the results under plausible non-missing at random situations.

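### SAP 2.6.5 assumes missing 6MWT data are MAR, but no planned 6MWD analysis uses that assumption, and the observed-case means can be biased under it

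*SAP*

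**What the plan says.** - **Assumption.** SAP 2.6.5, under sensitivity analyses: "For the analysis of 6MWT, missing measurement will be assumed MAR". It continues: "Alternative assumptions may be explored to investigate the robustness of the results under plausible non-missing at random situations". No method is named for either sentence.
- **6MWD analysis.** SAP 2.6.1.1: "Test performed at baseline and at visits on Day 176 and 358 will be used for analysis". The output is descriptive statistics "summarizing 6MWD parameters and their changes from baseline will be summarized by visit/time for treatment group assigned in the parent study and overall", with spaghetti plots and listings. A comparison of the parent-study groups is also announced, without a method.
- **Imputation.** SAP 2.6.4: "If not specified, missing data will not be imputed". Nothing is specified under 6MWD.
- **Models.** SAP 2.6.2: "Most analyses will be conducted descriptively using summary statistics". The only opening for models is the time-to-clinical-worsening endpoint (TTCW): "statistical models may be used when data allows for TTCW". SAP 5.4, on statistical models, is marked not applicable.
- **Protocol.** Section 9.4.1 also plans descriptive summaries of change in 6MWD.
- **Early stopping.** Protocol 1.3 asks participants who stop study treatment to attend the EOT visit as soon as possible, and Table 1-2 lists the 6MWT in the EOT column, which is the Week 52 visit. The SAP has no rule on whether such a walk is analysed as Day 358.

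**The concern.** MAR allows the chance of a missing walk to depend on what was already observed, such as the Week 26 distance. An analysis that relies on MAR has to use those earlier values, through a likelihood model, multiple imputation or weighting. A by-visit mean of the walks performed uses none of them. In general it is unbiased only if missingness is unrelated to the Week 52 change. So SAP 2.6.5 states an assumption that the analysis does not use, and its not-at-random exploration has no MAR estimate to depart from.

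There is no control arm. Protocol 1.1 says the study should help decide whether LTP001 merits further development, and section 4.1 lets observed efficacy inform continuation. If the participants without a Week 52 walk are mainly those who were declining, a stable mean 6MWD could partly reflect who is left.

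**Working it through.** **Step 1: is there an analysis that uses MAR?** SAP 2.6.1.1 gives summaries, plots and listings. SAP 2.6.4 rules out unspecified imputation. SAP 2.6.2 confines models to TTCW, and SAP 5.4 lists none. The 6MWD means are therefore observed-case.

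**Step 2: what do the documents say about size?** They give no figure to reproduce. Sample size is marked not applicable (protocol 9.9, SAP section 3), and no SD, correlation, dropout rate or expected change in 6MWD is stated. All inputs below are assumptions, apart from n = 40, which is the protocol's approximate number of participants.

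**Step 3: closed form, hard selection.** Suppose the worst fraction d at Week 26 all lack a Week 52 walk, and the Week 26 and Week 52 changes have correlation ρ and equal SD. Then

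bias of the observed-case mean, in SD units = ρ × φ(z_d) / (1 − d).

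| d | φ(z_d) | φ(z_d)/(1 − d) | ρ = 0.5 | ρ = 0.8 |
|---|---|---|---|---|
| 0.10 | 0.1755 | 0.195 | 0.10 | 0.16 |
| 0.20 | 0.2800 | 0.350 | 0.18 | 0.28 |
| 0.30 | 0.3477 | 0.497 | 0.25 | 0.40 |

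In metres at ρ = 0.7 and SD 60 m, multiply the third column by 0.7 × 60 = 42. This gives 8.2, 14.7 and 20.9 m.

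**Step 4: simulation, gentler selection.** Settings: n = 40, true change 0, ρ = 0.7, SD 60 m, 20,000 runs. Dropout is logistic in the Week 26 change, with a log-odds slope of 1.5 per SD in either direction, or zero. All three missingness patterns are MAR. Entries are bias in metres.

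| Who misses Week 52 | Estimate | 10% | 20% | 30% |
|---|---|---|---|---|
| Worse at Week 26 | Observed-case | +5.2 | +9.6 | +13.8 |
| Unrelated to walk (MCAR) | Observed-case | 0.0 | −0.1 | 0.0 (−0.05) |
| Better at Week 26 | Observed-case | −5.1 | −9.6 | −13.7 |
| Worse at Week 26 | Regression on Week 26 (MAR-valid) | 0.0 | +0.1 | 0.0 |
| Worse at Week 26 | Early EOT walk counted as Week 52 | −2.0 | −3.2 | −4.1 |

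The last row takes the early EOT walk to equal the Week 26 value. With 20% missing and worse participants leaving, the spread of the estimates was 10.4 m for the regression and 10.2 m for the observed-case mean, so the correction costs little precision.

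**Step 5: range when worse participants leave.** Over d = 10 to 30%, ρ = 0.5 to 0.9 and SD 40 to 80 m, the observed-case bias is +2.4 to +23.4 m under logistic dropout and +3.9 to +35.8 m under hard selection.

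**The case against.** A reader might infer that the Week 52 mean change is biased upward under the SAP's own assumption. The documents do not support that. MAR fixes neither the presence nor the sign of bias: MCAR is a special case with none, and MAR loss of better walkers biases the mean downward. Upward bias needs the further assumption that worsening participants have no Week 52 walk.

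The evidence on that assumption points both ways.

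- **For:** protocol 7.1 requires treatment to stop in several situations of PAH deterioration. The minimum data after stopping can be collected by telephone or email and include no walk. Table 1-2 makes the 6MWT on-site only.
- **Against:** participants who stop treatment are asked to attend an early EOT visit at which the 6MWT is scheduled, and protocol 4.3.1 lets some who need escalated therapy stay on drug after discussion with the sponsor.

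Two limits on the arithmetic also stand. Hard selection is the harshest pattern at a given dropout rate, and logistic dropout gives about two thirds of it (5.2/8.2 = 0.63; 13.8/20.9 = 0.66). The near-zero bias of the regression estimate follows from simulating MAR data with every Week 26 value observed, so it says nothing about not-at-random loss or about participants who leave before Week 26.

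It is also fair to say that attrition would be visible. N by visit, individual plots, discontinuation reasons and TTCW are all reported. That helps the reader but does not correct the mean. Deleting the MAR sentence and reporting missing counts with reasons would remove the contradiction, but would likewise leave the mean uncorrected.

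Finally, 6MWD is a secondary, descriptive endpoint with no hypothesis test in a safety study. That limits the weight of the point without answering it.

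**Conclusion.** The inconsistency stands: SAP 2.6.5 assumes MAR, and no planned 6MWD analysis uses it. The observed-case means can be biased under that assumption, and upward is the likelier direction if worsening participants lack a Week 52 walk. The documents determine neither the direction nor the size.

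As an illustration only, the bias is about 0.1 to 0.4 SD under hard selection of the worst 10 to 30% with a correlation of 0.5 to 0.8. It is less with gentler dropout, and absent or reversed if early EOT walks count as Week 52. The unwritten rule on early EOT walks therefore matters as much as the missing model, because it can change the sign of the bias. The plan should be amended, in proportion to a secondary descriptive endpoint.

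**What to change.** 1. **SAP 2.6.1.1:** keep the observed-case table and add beside it a MAR-based estimate of change in 6MWD. A mixed model for repeated measures would serve, using the parent-study baseline, the parent-study EOT, Week 26 and Week 52, with terms for visit, parent arm, visit-by-arm and baseline, and a simple covariance structure. Including the parent-study EOT walk gives participants who leave before Week 26 an earlier value to draw on.
2. **SAP section 4:** list this model as an addition to the descriptive analysis in protocol 9.4.1. Align SAP 2.6.2 and 5.4, which at present leave no room for it.
3. **Visit assignment:** state whether a 6MWT at an early EOT visit is analysed at its actual time or as Day 358.
4. **SAP 2.6.5:** replace the optional exploration with one named not-at-random check, for example a stated downward shift applied to missing Week 52 values.

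The cost is SAP wording and one model on data already collected. The downside is that about 40 participants will support only a simple covariance structure.
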